### **2.2 Secondary Objectives**

- To examine adherence to and timeliness of injections over time among adolescent participants who are provided CAB LA and information regarding its safety and unknown efficacy.
- To examine patterns of sexual risk behavior over time among adolescent participants who are provided CAB LA and information regarding its safety and unknown efficacy.
- To evaluate the safety of CAB LA for 48 weeks of follow-up after final injection.
- To characterize the pharmacokinetics of CAB LA.

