# **6.0 SAFETY MONITORING AND AE REPORTING**

## **6.1 AE Definition and Reporting**

An AE is defined as any untoward medical occurrence in a clinical research participant administered an investigational product and which does not necessarily have a causal relationship with the investigational product. As such, an AE can be an unfavorable or unintended sign (including an

abnormal laboratory finding, for example), symptom or disease temporally associated with the use of an investigational product, whether or not considered related to the product.

Study participants will be provided a 24-hour telephone number and contact information and instructed to contact the study clinician to report any AEs they may experience. For life-threatening events, they will also be instructed to seek immediate emergency care. Where feasible and medically appropriate, participants will be encouraged to seek evaluation where the study clinician is based, and to request that the clinician be contacted upon their arrival. With appropriate permission of the participant, whenever possible, records from all non-study medical providers related to AEs will be obtained and required data elements will be recorded on study CRFs. All participants reporting an AE will be followed clinically, until the AE resolves (returns to baseline) or stabilizes.

Study site staff will document in source documents and the appropriate CRF all AEs [Grade 1 and higher, and any AE that leads to a study product hold (temporary or permanent) will be captured on CRFs] reported by or observed in enrolled study participants, regardless of severity and presumed relationship to study product. AE severity will be graded per the DAIDS Table for Grading Adult and Pediatric Adverse Events, Corrected Version 2.1, July 2017. This version will be used for the entire duration of the study.

The AE reporting period for this study is from Enrollment (Week 0) until follow-up in the study ends.

Relatedness is an assessment made by a study clinician of whether or not the event is related to the study agent. The relationship of all AEs to study product will be assessed as specified in Version 2.0, January 2010 of the DAIDS EAE Reporting Manual.

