### **7.2.2 Secondary Endpoints**

- Plasma CAB pharmacokinetics
- Proportion of participants experiencing Grade 2 or higher clinical AEs and laboratory abnormalities in the oral phase and the aggregate over the entire study period
- Proportion of injection visits that occurred “on-time”
- Change from enrollment of self-reported sexual behavior (number of sexual partners, increased episodes of unprotected anal intercourse) during the study period

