2.2 Study Objectives and Endpoints

Primary objectives:

- To evaluate the safety, tolerability, and acceptability of CAB LA in healthy, HIV-uninfected male adolescents aged below 18 years.

Secondary objectives:

- To examine adherence to and timeliness of injections over time among adolescent participants provided CAB LA and information regarding its safety and efficacy.
- To examine patterns of sexual risk behavior over time among adolescent participants provided CAB LA and information regarding its safety and efficacy.
- To evaluate the safety of oral CAB during step 1 (oral phase) as well as all study products during the aggregate oral+injectable period for all enrolled participants. Additionally, we will include an intention to treat analysis for the primary safety endpoint.
- To characterize the pharmacokinetics of CAB LA
- Additional exploratory analyses will be done with the laboratory and clinical data, including resistance mutations

To achieve the primary and secondary objective, the planned primary and secondary endpoints are:

Primary endpoints:

Safety endpoint: Proportion of participants experiencing any Grade 2 or higher clinical adverse events (AEs) and laboratory abnormalities among participants who receive at least one injection of CAB LA. Laboratory abnormalities include grade 2 or above on tests include (CRF: Chemistry Panel, Fasting Lipid Test Results, Urinalysis, Hematology):

- Renal function: Creatinine, Creatinine clearance
- Hematology: Hemoglobin, Platelets, WBC, Neutrophils, Lymphocytes
- Liver function: Alkaline phosphatase, AST, ALT, Total bilirubin
- Electrolytes: Phosphorus, Calcium
- Other chemistries: CPK, Glucose, Amylase, Lipase,
- Urine test: Protein, Glucose
- Fasting Lipid Test Results: Total cholesterol, Triglycerides, LDL, HDL

Tolerability endpoint: Proportion of participants who receive at least 1 injection and who discontinue receiving injections prior to the full course of injections due to intolerance of injection, frequency of injections or burden of study procedures. Reasons for intolerance may include:

- Injection site reaction
- Participant refused further participation¹
- Participant lost to follow-up
- Participant is unwilling or unable to comply with required study procedures
- Participant refused further study product use
- Participant unable to adhere to visit schedule

¹Excluding cases in which reason for termination is unrelated to intolerance

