3. GENERAL DATA ANALYSIS CONSIDERATIONS

3.1 Analysis Set(s)

Primary and secondary analyses will be carried out among the following populations:

Screened Population: Includes all participants who were screened for potential enrollment.

Injection Population: Includes enrolled participants who receive at least one injection of CAB LA.

Safety Population: Includes enrolled participants who began step 1 (oral phase).

Enrolled Population: Includes all enrolled participants.

Seroconverter Population: Includes all enrolled participants who seroconverted during the study.

TDF/FTC Population: All enrolled participants who were provided TDF/FTC during the study.

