3.2 Statistical Analysis Issues

AEs will be tabulated using MedDRA preferred terms. The number and percentage of participants experiencing each specific AE (All AEs, Grade 2 or higher, and SAEs) will be tabulated by severity and by relationship to study product. For the calculations in these tables, each participant's AEs will be counted once as the maximum severity and relationship to study product. AEs leading to temporarily or

permanently stopping drug will also be summarized. Methods for imputation of missing dates are described in Appendix C

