8.1 Safety endpoint analysis

Cohort: Injection population

Analysis description: Number and percent of participants experiencing any Grade 2 or higher clinical adverse events (AEs) or laboratory abnormalities (reported as adverse events) from the first injection visit to 8 weeks after the last Step 2 injection visit, or Week 41, whichever comes first. See Section 3.2 for details regarding aggregation and tabulation of AEs.

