12.1 Plasma CAB pharmacokinetics

Analysis details are provided in the current version of the Pharmacokinetics Analysis Plan

12.2 Proportion of participants experiencing Grade 2 or higher clinical AEs and laboratory abnormalities in the oral phase and over the entire study period

Cohort: Safety population

Analysis description: Number and percent of participants experiencing any Grade 2 or higher clinical adverse events (AEs) or laboratory abnormalities from:

1. enrollment to week 5 (oral phase (step 1), including interim visits).
2. enrollment to 8 weeks following the last injection received (aggregate over oral+injection phases (step 1-step 2) including interim visits)

12.3 Proportion of participants receiving one or more injections who experience Grade 2 or higher clinical AEs and laboratory abnormalities from initial injection to 36 weeks later

Population: Injection population

Analysis description: Number and percent of participants experiencing any Grade 2 or higher clinical adverse events (AEs) or laboratory abnormalities from the first injection visit to approximately 36 weeks later regardless of whether participants received all 5 injections. For participants receiving all 5 injections, the end date is 8 weeks following the week 33 injection visit. For participants discontinuing study product early and moving on to Step 3, the end date is 36 weeks after the initial injection. Participants who terminate early are included in the analysis and censored at the date of termination.

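### The SAP drops the protocol's 48-week post-injection safety objective and closes every dated Grade 2+ window by about Week 41, while the protocol windows that run to Week 81 mix continued CAB LA with washout

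*SAP*

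**What the plan says.** Protocol 2.2 lists as a secondary objective "To evaluate the safety of CAB LA for 48 weeks of follow-up after final injection". Protocol 7.2.2 sets the secondary Grade 2+ endpoint "in the oral phase and the aggregate over the entire study period", and SAP 2.2 repeats that wording. Protocol 6.1 collects the data needed: "The AE reporting period for this study is from Enrollment (Week 0) until follow-up in the study ends".

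The SAP's analyses are narrower:

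- SAP 2.2 has no 48-week objective. Its secondary safety objective is "To evaluate the safety of oral CAB during step 1 (oral phase) as well as all study products during the aggregate oral+injectable period".
- SAP 8.1 counts events "from the first injection visit to 8 weeks after the last Step 2 injection visit, or Week 41, whichever comes first".
- SAP 12.2 is headed as covering the whole study, but its second window is "enrollment to 8 weeks following the last injection received (aggregate over oral+injection phases (step 1-step 2) including interim visits".
- SAP 12.3 ends 8 weeks after the Week 33 injection for participants with all five injections, and 36 weeks after the first injection for those who stop early and enter Step 3.
- SAP Appendix A limits the listings of adverse events of special interest to Steps 1 and 2.
- SAP 3.1 defines a population as "All enrolled participants who were provided TDF/FTC during the study", but no analysis in the SAP is assigned to it.

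Two protocol windows go further. Section 7.7.1 runs to 48 weeks after the last injection, and 7.8.2 includes the follow-up period. Each gives one pooled proportion. In Step 3, however, participants choose between CAB LA every 8 weeks and oral TDF/FTC, and may move from TDF/FTC to CAB LA without lengthening Step 3 (Protocol 5.7).

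**The concern.** The depot cannot be removed. Protocol 1.10 expects detectable drug for a year or more, and Protocol 1.5.2 reports a median of 42.7 weeks to undetectable levels in adult men, with 22% still detectable at 60 weeks. Safety during that decline is a stated objective, yet the SAP gives it no window and SAP 12.2 does not deliver what its own heading and endpoint promise. The choice of which Step 3 events to show, and how, is then left until the data are known.

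Returning to the protocol windows would not settle it. In the same calendar weeks, one participant may be receiving injections and another may be in washout on TDF/FTC. A single proportion describes neither.

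**Working it through.** **Inputs.** Step 2 injections at Weeks 5, 9, 17, 25 and 33, and follow-up to 48 weeks after the last Step 2 injection (Protocol 2.3); window rules from SAP 8.1, 12.2 and 12.3; Step 3 schedules from Protocol Appendices III and IV; nine enrolled (SAP 6.4).

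**The SAP's own end point.** 33 + 8 = Week 41, and 5 + 36 = Week 41. These agree with the Week 41 cap in 8.1 and the roughly 36 weeks in 12.3.

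**The gap for a five-injection participant.** Follow-up ends at 33 + 48 = Week 81. Covered: 41 − 33 = 8 weeks, 8/48 = 17%. Not covered: 81 − 41 = 40 weeks, 40/48 = 83%.

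**All participants, by last Step 2 injection.** Coverage by 12.3 is 41 minus the week of the last injection; the remainder is 48 minus that.

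| Last injection (week) | 8.1 and 12.2 close | 12.3 closes | 48 weeks end | Weeks covered by 12.3 | Weeks outside every dated window |
|---|---|---|---|---|---|
| 5 | 13 | 41 | 53 | 36 | 12 |
| 9 | 17 | 41 | 57 | 32 | 16 |
| 17 | 25 | 41 | 65 | 24 | 24 |
| 25 | 33 | 41 | 73 | 16 | 32 |
| 33 | 41 | 41 | 81 | 8 | 40 |

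**The conflict inside 12.2.** The table applies its Step 1 to Step 2 parenthetical. If the reference to the last injection received were taken literally, a Step 3 continuer last dosed at +40 (Week 73) or +48 (Week 81) would be followed to Week 81 or 89. A TDF/FTC user would still stop at Week 41. Window length would then depend on the product chosen.

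**Pooling in the protocol windows.** After a Week 33 injection, the Step 3 slots in Appendix IV fall at Weeks 41, 49, 57, 65, 73 and 81. For a continuer, Weeks 41 to 81 are dosing time; for a TDF/FTC user they are washout. A last Step 3 dose at +8, +16, +24, +32, +40 or +48 leaves only 40, 32, 24, 16, 8 or 0 weeks of follow-up.

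**Scheduled laboratory tests after Week 41** (five-injection participant; early-discontinuation column excluded):

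| Test | Oral schedule | Injection schedule |
|---|---|---|
| Liver function | 4 (+12, +24, +36, +48) | 2 (+24, +48) |
| Chemistry other than creatinine (7 analytes) | 0 | 2 (+24, +48) |
| Blood count | 2 (+24, +48) | 2 (+24, +48) |
| Urinalysis | 2 (+24, +48) | 0 |

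The chance of detecting a laboratory abnormality differs by product in both directions.

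**Precision.** With 0 events in 9, the exact two-sided 95% upper limit is 1 − 0.025^(1/9) = 0.336, or 34%. If the nine split 5 and 4 by product (an assumption), the limits are 52% and 60%.

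**The case against.** The strongest reply is that Step 3 safety is not absent from the SAP, and several parts of it stand.

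- SAP 12.3 names Step 3 and covers part of it for early stoppers. A reader might infer that the drug-resistance analysis in 12.6 is the only safety-related analysis to name Step 3; the documents do not support that.
- A reader might also infer that no Step 3 injection can fall in a dated window. That is true only of participants who complete Step 2. Someone whose last Step 2 injection was at Week 5 and who later moves to CAB LA has slots at Weeks 13, 21, 29 and 37, all before 12.3 closes. The same possibility mixes on-drug and off-drug time inside 12.3.
- SAP 3.2 has no end date: "The number and percentage of participants experiencing each specific AE (All AEs, Grade 2 or higher, and SAEs) will be tabulated". SAP 9.2 sets no end date for its laboratory summaries, and SAP 9 points to a closed DSMB report described in a separate plan. All may include Step 3 events. None is tied to the 48-week objective or split by product in use.
- Protocol 7.7.3 summarises events that are treatment emergent during injectable dosing, and lists expedited reports with time since the last injection. Serious events can therefore be placed against dosing. Non-serious Grade 2+ events get no such placement, and continuers are not separated from participants in washout.
- The TDF/FTC population may serve the separate pharmacokinetic plan, so its lack of use in the SAP is only weak evidence of an omission.
- Version 2.0 was revised because of the Step 3 CAB LA option, and the 8.1 window does avoid pooling. The change history does not say the objective was withdrawn, and mixed exposure calls for a split.
- With at most nine participants, elaborate rules for tail time would be out of proportion. That is right, and it limits the fix.

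**Conclusion.** The point holds as a mismatch between protocol and SAP, and between SAP 12.2 and its own heading. Every dated Grade 2+ window closes by about Week 41. That leaves 40 of 48 post-injection weeks outside for a five-injection participant, and 12, 16, 24 or 32 weeks for someone whose last Step 2 injection was at Week 5, 9, 17 or 25. The figures assume on-schedule injections, the Step 1 to Step 2 reading of 12.2, and a 48-week clock that starts at the last Step 2 injection.

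The finding concerns dated windows. It does not show that Step 3 events go uncollected or unreported, since the undated tables may include them. Nor are oral-PrEP participants simply tested less: they have fewer chemistry analytes but more liver tests, plus urinalysis. The pooling problem arises only if the protocol windows are reported. The SAP should be corrected, but the result will be descriptive whatever is done.

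**What to change.** In the SAP:

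1. Restore the 48-week objective in 2.2.
2. Extend 12.2 to study exit, or relabel it as covering the oral and injection phases only. Remove the conflict over which last injection is meant.
3. Add one descriptive Step 3 summary and listing of Grade 2+ events and SAEs by product in use at onset (CAB LA, TDF/FTC or neither), with time since the most recent CAB LA dose.
4. Split or censor any window that reaches Step 3, including those in Protocol 7.7.1 and 7.8.2 if reported, at the first Step 3 CAB LA injection.
5. State that the results are descriptive only, and that laboratory schedules differ by product.

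The cost is one SAP revision, one table and one listing, with no new visits or tests. Making the change in the SAP avoids a protocol amendment and the approvals that Protocol 10.5 requires. It should be made before database lock, or labelled as added later. The downside is very small groups, so the listing will carry most of the information.

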5. GENERAL ANALYSIS METHODS

[figure not shown]
Within the single arm, all primary and secondary outcome proportions with 95% CIs will be calculated.

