12. SECONDARY ANALYSES

For binary secondary endpoints, the number and proportion of endpoints will be computed along with corresponding 95% confidence intervals. Each summary will be provided both overall and by site. CSR analysis will be only summarized overall. Endpoint descriptions are available in section 2.2.

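### SAP 12.3 says early terminators are censored but reports a crude percent, so anyone who leaves event-free counts as a 36-week non-event and the figure, read as 36-week risk, can only err low

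*SAP*

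**What the plan says.** SAP 12.3 uses the injection population (SAP 3.1: "Injection Population: Includes enrolled participants who receive at least one injection of CAB LA") and defines its result as "Number and percent of participants experiencing any Grade 2 or higher clinical adverse events (AEs) or laboratory abnormalities from the first injection visit". The window is fixed at about 36 weeks and does not depend on how many injections were given. The section then sets three follow-up rules:

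- Participants who receive all five injections are followed to 8 weeks after the Week 33 injection visit, which is 36 weeks after Week 5.
- Those who stop product but stay in the study keep the full window: "For participants discontinuing study product early and moving on to Step 3, the end date is 36 weeks after the initial injection".
- For those who leave the study: "Participants who terminate early are included in the analysis and censored at the date of termination".

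The methods sections offer one kind of statistic. SAP 5 states: "Within the single arm, all primary and secondary outcome proportions with 95% CIs will be calculated". The opening of SAP 12 states: "For binary secondary endpoints, the number and proportion of endpoints will be computed along with corresponding 95% confidence intervals". Protocol 7.7.1 gives exact binomial intervals for safety endpoints. SAP Appendix C imputes missing dates, not missing outcomes. No Kaplan-Meier, cumulative-incidence or person-time method appears in either document.

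**The concern.** Censoring means that a participant contributes information up to a date and none after it. That needs an estimator with a changing risk set or a person-time denominator. A count divided by N has neither, so the instruction has no effect on the denominator. Someone who leaves event-free at week 8 carries the same weight as someone observed event-free for 36 weeks.

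Two things are at stake. First, the text can be programmed in two ways, as a plain proportion or as a survival estimate, and these give different numbers. Second, if the percent is read as the risk over the 36 weeks named in the section's title, short follow-up is taken for safety. Leaving may not be neutral either: SAP 2.2 lists refusal of further participation and loss to follow-up among possible reasons for intolerance.

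**Working it through.** **The plan's own figure.** SAP 12.3 states none. The only planning figure for proportions is SAP 2.5, Table 2. With half-width 1.96·√(p(1−p)/50), p = 0.1, 0.2, 0.3, 0.4, 0.5 gives 0.083, 0.111, 0.127, 0.136, 0.139, which matches the table to its rounding. This confirms planned precision only and says nothing about censoring.

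**Direction and limit (no rate assumed).** Let x be the participants with an observed event, k those who left before 36 weeks without one, and N the injection population. Events seen before leaving are a subset of events by 36 weeks. In the same participants, full follow-up would therefore give a proportion between x/N (none of the k would have had an event) and (x+k)/N (all would). The crude percent sits at the lower end whether or not leaving is informative.

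- Shortfall if k = 0: zero.
- Most that one such participant can add: 1/9 = 11.1 points at N = 9; 1/50 = 2.0 points at N = 50. Nine is total accrual (SAP 6.4), so N is at most 9.

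**Constructed example.** N = 9 and x = 4, with events evenly spaced at weeks 4.5, 13.5, 22.5 and 31.5 after first injection. The crude result is 4/9 = 44.4% (exact 95% CI 13.7% to 78.8%) whatever k is.

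| k | Kaplan-Meier at 36 weeks, leaving at week 30 / week 4 | Bounds |
|---|---|---|
| 0 | 44.4% | 44.4% |
| 1 | 46.7% / 50.0% | 44.4% to 55.6% |
| 2 | 50.0% / 57.1% | 44.4% to 66.7% |

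For k = 1 leaving at week 4, eight remain at risk at the first event, so the estimate is 4/8 = 50.0%.

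**Illustrative expected shortfall.** The documents give no study-termination rate and no expected Grade 2 or higher rate, so both are assumed here. With a constant hazard, true 36-week risk p, and a share d leaving at times uniform over 0 to 36 weeks, the chance of an event before leaving is q = 1 − p/(−ln(1−p)), and the shortfall is d·(p − q).

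| p | q | d = 5% | d = 1/9 | d = 25% |
|---|---|---|---|---|
| 0.3 | 0.159 | 0.7 | 1.6 | 3.5 |
| 0.5 | 0.279 | 1.1 | 2.5 | 5.5 |
| 0.7 | 0.419 | 1.4 | 3.1 | 7.0 |
| 0.9 | 0.609 | 1.5 | 3.2 | 7.3 |

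(Shortfalls in percentage points.)

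**Heavier, earlier loss.** If m of 9 leave at week w, the expected crude value is [(9−m)p + m(1 − e^(−hw))]/9, with h = −ln(1−p)/36.

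- p = 0.7, m = 2, w = 8: 0.597, or 10 points low.
- p = 0.7, m = 3, w = 12: 0.577, or 12 points low.
- p = 0.5, w = 12: 0.435 for m = 2 and 0.402 for m = 3, or 6.5 and 9.8 points low.
- One leaver at week 12: 4.1 points (p = 0.7) or 3.3 points (p = 0.5).

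**The case against.** The best defence is that the word is loose but the analysis is ordinary. The two sentences before it set end dates, and this one can be read as a third: count events up to termination. The result is then an observed proportion, a usual safety summary, and correct under that name. This reading stands as far as it goes. It does not remove the shortfall against the 36 weeks in the section's title, and the SAP does not give the result that name.

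Several stronger readings are tempting, and the documents do not support them:

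- *All early terminators count as event-free.* They do not. They are included, so an event before leaving is counted.
- *The percent is biased low.* Only if at least one person leaves event-free before 36 weeks.
- *Everyone who stops injections is affected.* Those who enter Step 3 are followed to 36 weeks and are unaffected while they remain in the study. The HPTN 077 figures in Protocol 1.5.2 (89% injected at least once, 75% completing all injections) concern injection completion, so they are not a study-termination rate.
- *The shortfall is 6.5 to 12 points.* That rests on two or three of nine leaving by week 8 or 12. Constant hazard is also doubtful, because Protocol Appendix II puts four of the ten Step 2 visits in the first five weeks after first injection. If detection follows visits instead, the four scenarios above with two or three leavers give 7.1, 8.3, 4.6 and 6.9 points.
- *SAP 12.3 exists to repair SAP 8.1.* The primary window ends "8 weeks after the last Step 2 injection visit, or Week 41, whichever comes first". That is 8 weeks at risk after one injection (Week 5 to 13) and 36 after five (Week 5 to 41), a window tied to exposure by design. SAP 2.2 announces an intention-to-treat analysis of the primary safety endpoint, and 12.3 appears to be it, but the SAP does not say so.

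It is also fair that this is a secondary analysis in a single arm with no comparator or threshold, and that the exact interval for 4/9 is about 65 points wide.

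**Conclusion.** The point holds in limited form. SAP 12.3 states a censoring rule that no planned estimator uses, so participants who terminate event-free are scored as 36-week non-events. As a measure of 36-week risk the percent can err in one direction only, low. The limit of k/N needs no assumption about why or when people leave. The 1 to 7 point range assumes a constant hazard, 36-week risks of 0.3 to 0.9 and uniform leaving by 5% to 25%; the figures up to about 12 points assume heavier and earlier loss. The actual size cannot be computed from the documents and may be zero. It is probably small beside the sampling uncertainty at N of at most 9, but each event-free leaver matters far more there than at the planned 50. A correction is worthwhile because it is cheap and removes an ambiguity in programming.

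**What to change.** In SAP 12.3, replace the censoring sentence with a statement of what is estimated, and report:

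1. the crude number and percent, labelled as observed incidence, with an exact binomial 95% CI in line with Protocol 7.7.1;
2. k, the number who left before 36 weeks without a qualifying event;
3. the bounds x/N to (x+k)/N;
4. the Kaplan-Meier cumulative incidence at 36 weeks from first injection with a CI, noting that it assumes non-informative termination, which is doubtful if participants leave because of intolerance.

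With so few participants, items 2 and 3 are the most informative because they need no such assumption. A person-time rate beside SAP 8.1 is optional.

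The cost is a few lines of SAP text and programming. The downside is wide intervals with at most nine participants.
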